8.0 Statistical Considerations and Evaluation of Results

This trial will determine whether epigenetic priming may enhance the effects of PD-1 inhibitors in patients with ER+ metastatic breast cancer who have progressed on prior hormone therapy and chemotherapy. The trial will contain three arms. Within each arm we will determine whether epigenetic priming will required prolonged pre-exposure to epigenetic modulators or concomitant administration.

Three arms will be tested, with each independent assessment. Patients will be stratified by prior number of hormonal therapy and chemotherapy, then randomized across arms by [name], UCSF.

8.1 Response rates to chemotherapy in breast cancer are less than 20%. Historical response rates to pembrolizumab and MPDL3280A have been 18% and 19%, respectively, in patients whose tumors are PD-L1 positive. Hence, we expect the response rate for unselected patients and patients with no PD-L1 expression would be 10% or less. In contrast, we anticipate that vorinostat will increase the response rate to 30%**Sample Size and Power Estimate**

Response rates to hormonal therapy and MTOR or HDAC inhibitors have been reported as 5-20% (19% for VOR-Tam, 6% for entinostat-exemestane, 12% for exemestane-everolimus). Given the recent additions to hormonal therapy this trial will treat a patient population that has received more lines of therapy than these trials, however we are interested in an ORR of >30%.

8.2 For each arm: Using an Optimal Simon's two-stage design (Simon, 1989), the null hypothesis (H₀) that the true response rate is 10% will be tested against a one-sided alternative. In the first stage, 10 patients will be accrued and a decision will be made to continue or stop accrual based on the observed objective response rate (ORR). If there are 0 or 1 objective responses at 24 weeks in these 10 patients, accrual to this arm of the study will be stopped. Otherwise, 19 additional patients will be accrued for a total of n=29. We estimate that each regimen under evaluation will achieve ORR ≥ 30%. This study is designed to have an alpha of 0.0471, and a power of 80.5% to test the null hypothesis H₀: ORR = 10% against an alternative hypothesis, H_A: ORR = 30%, where ORR is defined as CR, PR, or SD ≥ 24 weeks where arms are enrolled independently.**Interim Analyses**

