8.3.2 Evaluation of Efficacy

For each arm objective response rate (ORR) will be defined as the proportion of participants randomized to that arm whose status is SD or better (CR, PR) at 24 weeks' follow-up. In addition to calculating the ORR, we will calculate the corresponding Agresti-Coull interval 95% confidence interval (CI) (Ref: *Agresti, Alan; Coull, Brent A. (1998). "Approximate is better than 'exact' for interval estimation of binomial proportions". The American Statistician 52: 119–126. doi:10.2307/2685469*). If the lower bound of the 95% CI exceeds 10%, we will reject the null

hypothesis that the regimen is ineffective and conclude that it is sufficiently effective to warrant further study.

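### The written success rule needs 7 of 29 responders, but the stated alpha of 0.0471 and power of 80.5% belong to a 6-of-29 rule; power as written is 73.9%

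*Combined protocol and SAP*

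**What the plan says.** Section 8.2 applies the optimal Simon design to each arm. The null hypothesis is "that the true response rate is 10% will be tested against a one-sided alternative", and the alternative response rate is 30%. The stage 1 rule is explicit: "If there are 0 or 1 objective responses at 24 weeks in these 10 patients, accrual to this arm of the study will be stopped". An arm that passes this stage goes on to enrol a further 19, which brings it to 29. The section then states the operating characteristics: "This study is designed to have an alpha of 0.0471, and a power of 80.5% to test the null hypothesis". It does not say how many responders among the 29 lead to rejection.

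Section 8.3.2 defines the response rate in each arm as the proportion of randomized participants with stable disease or better at 24 weeks, and attaches a 95% Agresti-Coull confidence interval. It uses that interval for the decision: "If the lower bound of the 95% CI exceeds 10%, we will reject the null" hypothesis, and the regimen is then judged worth further study. No other final rule appears in the plan.

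**The concern.** A Simon design has two boundaries, and its alpha and power depend on both. Here the second boundary is missing from the design section, and the analysis section supplies a different kind of rule: the lower limit of a two-sided 95% interval. Such a limit is close to a one-sided test at 2.5%, whereas section 8.2 claims a one-sided alpha of nearly 5%. The written rule is therefore likely to be stricter than the one behind the claimed figures.

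This is the primary efficacy decision, and it is made separately in each arm. If the rules differ, the stated power is not the power the trial has. The result for an arm at the boundary would also depend on which section the analyst follows. The trial is open-label, so that choice could be made with the result in view.

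**Working it through.** **Inputs.** From section 8.2: p0 = 0.10, p1 = 0.30, n1 = 10, stop at 0 or 1 responses, n = 29 (10 + 19), alpha 0.0471, power 80.5%. From section 8.3.2: Agresti-Coull 95% interval, reject if the lower limit exceeds 10%. From section 8.3.1: all randomized patients are analysed, so the planned denominator is 29 per arm.

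**Step 1: reproduce the stated figures.** Let X1 be the responders among the first 10 and X2 those among the next 19. With rejection at r or more of 29, the exact probability of rejection at true rate p is

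P(reject) = Σ over x = 2 to 10 of P(X1 = x) × P(X2 ≥ r − x), with X1 ~ Bin(10, p) and X2 ~ Bin(19, p).

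For r = 6 and p = 0.30 the leading terms are:

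- x = 2: 0.23347 × 0.86683 = 0.20238
- x = 3: 0.26683 × 0.95378 = 0.25449
- x = 4: 0.20012 × 0.98958 = 0.19804
- x = 5: 0.10292 × 0.99886 = 0.10280
- x = 6 to 10 together: 0.04736

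The total is 0.8051, the stated 80.5%. The same sum for other cut-offs gives:

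| Reject at | Alpha (p = 0.10) | Power (p = 0.30) |
|---|---|---|
| ≥5 of 29 | 0.1016 | 83.7% |
| ≥6 of 29 | 0.0471 | 80.5% |
| ≥7 of 29 | 0.0177 | 73.9% |
| ≥8 of 29 | 0.0055 | 63.3% |

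Only 6 or more of 29 returns both stated figures.

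**Step 2: find the cut-off implied by section 8.3.2.** With z = 1.96, the Agresti-Coull lower limit uses ñ = n + z² = 29 + 3.84 = 32.84, p̃ = (x + z²/2)/ñ, and L = p̃ − z√(p̃(1 − p̃)/ñ).

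- x = 6: p̃ = 7.92/32.84 = 0.2412; standard error 0.0746; L = 0.2412 − 1.96 × 0.0746 = 0.0949. Not above 10%.
- x = 7: p̃ = 8.92/32.84 = 0.2716; standard error 0.0776; L = 0.2716 − 1.96 × 0.0776 = 0.1195. Above 10%.

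The written rule is therefore 7 or more of 29. The choice of interval does not change this. At 6 of 29 the lower limit is 9.62% with the add-2/add-4 version (z = 1.96), 9.85% with Wilson and 7.99% with Clopper-Pearson. At 7 of 29 all of these exceed 10%.

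**Step 3: operating characteristics of the written rule.** From the r = 7 row, alpha is 0.0177 and power is 73.9%. The power loss is 80.5 − 73.9 = 6.6 points, and type II error rises from 19.5% to 26.1%.

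**Step 4: how often the rules disagree.** They differ only when an arm passes stage 1 and ends with exactly 6 of 29 (20.7%). That probability is the difference between the r = 6 and r = 7 results: 0.0471 − 0.0177 = 2.9% at a true rate of 10%, and 80.5 − 73.9 = 6.6% at 30%. In between it is larger: 12.5% at a true rate of 20% and 10.8% at 25%.

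**The case against.** The arithmetic is not in dispute. The strongest arguments on the other side concern its weight.

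- **The error is conservative.** This is correct. The false-positive rate falls from 0.0471 to 0.0177, so no inactive regimen becomes more likely to advance. The stage 1 rule and the sample size are untouched. The cost falls entirely on power, which in a phase II screen means missing an active regimen.
- **The Simon cut-off is implied.** Also correct: the named design, its sample sizes, alpha and power together fix it at 6. But section 8.3.2 then writes a different rule for the same hypothesis, and nothing says which governs.
- **Section 8.3.2 does not say what follows when the bound is 10% or less.** This stands. An arm with 6 of 29 fails to reject the null; the plan does not say that such an arm must be called ineffective or dropped.
- **A one-sided 95% bound may have been meant.** Section 8.2 does specify a one-sided test, and the lower limit of a 90% interval at 6 of 29 is 10.86%, which would restore agreement. But the text names a 95% confidence interval, so the wording would have to change even if this was the intention.
- **The figures hold at exactly 29 patients.** This stands as a condition. Section 5.1.1.1 has patients with long early dose delays replaced, while section 8.3.1 analyses everyone randomized, so the denominator may move. Six responders pass the 95% rule at n = 27 (10.26%) and fail at n = 28 (9.86%).

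**Conclusion.** The inconsistency is real and affects the primary decision in each arm. The stated alpha of 0.0471 and power of 80.5% belong to rejection at 6 or more of 29. The only written rule requires 7 or more of 29, for which alpha is 0.0177 and power is 73.9%. The two disagree at a single outcome, 6 of 29, which has a 6.6% chance per arm at a true rate of 30%.

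This rests on the planned 29 patients per arm, on the stage 1 stop being applied as written, and on reading the interval as the two-sided 95% interval that the text names. The direction is conservative for type I error. It still needs to be corrected before analysis, because the plan claims a power that its own decision rule does not deliver.

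**What to change.** The preferred change is to state the final boundary in both 8.2 and 8.3.2: reject the null in an arm if at least 2 of the first 10 and at least 6 of 29 patients respond. Report the 95% Agresti-Coull interval as descriptive only. This makes the stated alpha and power correct.

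There are two alternatives:

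- Keep an interval rule but use the two-sided 90% Agresti-Coull interval. At n = 29 its lower limit is 8.34% for 5 responders and 10.86% for 6, so it gives the same cut. The match is not general: at n = 32, 6 responders give 9.78% and fail.
- Keep the 95% rule and restate alpha as 0.0177 and power as 73.9%.

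Whichever is chosen, say how the cut-off is set if the analysed number in an arm is not 29.

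The change is a sentence or two of text, with no added patients or data. Because it alters the primary decision rule, section 9.4 requires an amendment approved by the Protocol Review Committee and the CHR. If any arm already has response data, the amendment should record that the cut-off comes from the original design figures and not from those data.

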8.3.3 Evaluation of Safety

Analyses will be performed for all patients having received at least one dose of study drug. The study will use the NCI CTCAE v4.0.

8.3.4 Analyses of Exploratory Endpoints

8.3.4.1 Tissue based endpoints

Note: Tissue will be used for multiple different exploratory assays. In the event that there is insufficient tissue to perform all assays for an individual subject, the tissue should be prioritized for assays as follows, in which the first assay described is the highest priority.

Tumor PD-L1 assessment

PD-L1 protein expression on tumor tissue from pre-treatment and post-Cycle-3 biopsies, and any other tumor biospecimens obtained, will be evaluated immunohistochemically and scored on a scale of 0, 1, 2, or 3. This scoring will be used for the determination of relationships between tumor PD-L1 expression and clinical responses described above. Specifically, in addition to hypothesizing that delayed pembrolizumab treatment (i.e., Arm A) will increase tumor response, we hypothesize that (i) PD-L1 expression will stimulate tumor response, (ii) but will not be associated with treatment (because PD-L1 is stimulated by vorinostat not pembrolizumab).

For analysis, PD-L1 expression level, scored as {0,1,2,3}, will be classified as binary (0 =negative; 1-3 =positive); across two time-points, this defines four types of PD-L1 participants: {0,0; 0,1; 1,0; 1,1}. We will use logistic regression to estimate Cycle-6 tumor response rate (95% CI) as a function of study arm and PD-L1 level at baseline and Cycle 3. Either time-point will be eliminated from the model if its effect is weak ($p>0.2$), leaving two types of PD-L1 participants: either {0,0; 1,1} or {0,0; 0,1}.

Tissue immune subset quantification and localization

For all subjects, immune cell subsets and localization will be summarized by changes from baseline to after treatment using descriptive statistics.

Immune cell mRNA signatures of response

To identify individual genes whose expression levels at pre-treatment are associated with pCR, we will apply two-sample *t* tests to compare responders and non-responders. Adjusted P values controlling for false discovery rate (Benjamini and Hochberg method) will be derived. In addition, to assess association of pre-specified immune gene signature with response, the median expression level of the component genes will be used to represent the signature and two-sample *t* tests will be used. For genes or signatures that emerge as significantly associated with response, logistic regression models will be used to assess their independent association with response after adjusting for known clinical prognostic factors. To identify pharmacodynamic markers, paired *t*-test will be carried out to examine immune gene expression differences between pre-treatment and post treatment samples. Additionally, association of gene expression levels after epigenetic priming with long term efficacy outcomes, such as PFS and DFS, will be explored using the Cox proportional hazards regression model. Hierarchical clustering superimposed with response status, relevant baseline or prognostic characteristics or

experimental factors will be performed using Spearman correlation and complete linkage to visualize the discriminating power of the immune gene expression and the correlative structure among the genes and the samples.

T cell receptor (TCR) deep sequencing

The change in tumor-infiltrating TCR between pre-treatment and post-epigenetic priming will be assessed by calculating the number of unique clonotypes comprising the top 25th percentile of cumulative reads after sorting by clone abundance. Repertoire change between sequencing experiments will be measured using Morisita's distance. This analysis will also be performed in subjects receiving adjuvant chemotherapy using the same statistical techniques to evaluate the impact of adjuvant MPDL3280A on circulating T cell repertoire remodeling.

Genomic signatures of response

It is hypothesized that tumors with highly mutated or copy-aberrant genomes will either overexpress native proteins or express novel mutant proteins, both of which may be recognized by the immune system and serve as tumor-specific antigens. Therefore the effect of genomic mutations on the immune landscape will be investigated in each of the cohorts in this study as follows.

Tumor DNA will be isolated from pre-treatment tissue and from post-epigenetic priming specimens, and will be analyzed for copy number using the Human Genome CGH 244K Microarray (Agilent, Santa Clara, CA) and/or by next-generation sequencing. Results will be analyzed with DNA Analytics software (Agilent) and with the assistance of the UCSF Genome Core and the UCSF Biostatistics core. For copy number paired Wilcoxon signed-rank test will be applied to test difference of tumor gene copy number between pre and post treatment. Two-sample Wilcoxon signed-rank test will be used to test the gene copy number between tumor responders and non-responders for pre-treatment, post-treatment and changes before and after the treatment, separately. Multiple testing adjustment will be done by controlling false positive rate. Next-generation sequencing will take place using appropriate methods and biostatistical analyses. Annotation will be based on NCBI and UCSC databases. Chi-square test will be applied to obtain the significant variants associated with the clinical response.

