The PD-1 receptor-ligand interaction is a major pathway hijacked by tumors to suppress immune control. The normal function of PD-1, expressed on the cell surface of activated T-cells under healthy conditions, is to down-modulate unwanted or excessive immune responses, including autoimmune reactions. PD-1 (encoded by the gene *Pdcd1*) is an Ig superfamily member related to CD28 and CTLA-4, which has been shown to negatively regulate antigen receptor signaling upon engagement of its ligands (PD-L1 and/or PDL2)^{23,24}. The structure of murine PD-1 has been resolved²⁵. PD-1 and its family members are type I transmembrane glycoproteins containing an Ig Variable-type (V-type) domain responsible for ligand binding and a cytoplasmic tail, which is responsible for the binding of signaling molecules. The cytoplasmic tail of PD-1 contains 2 tyrosine-based signaling motifs, an immunoreceptor tyrosine-based inhibition motif (ITIM) and an immunoreceptor tyrosine-based switch motif (ITSM). Following T-cell stimulation, PD1 recruits the tyrosine phosphatases SHP-1 and SHP-2 to the ITSM motif within its cytoplasmic tail, leading to the dephosphorylation of effector molecules such as CD3 ζ , PKC θ and ZAP70, which are involved in the CD3 T-cell signaling cascade^{14,15,16,23}. The mechanism by which PD-1 down modulates T-cell responses is similar to, but distinct from that of CTLA-4 as both molecules regulate an overlapping set of signaling proteins^{26,27}. PD-1 was shown to be expressed on activated lymphocytes including peripheral CD4+ and CD8+ T-cells, B-cells, T regs and Natural Killer cells^{28,29}. Expression has also been shown during thymic development on CD4-CD8- (double negative) T-cells, as well as subsets of macrophages and dendritic cells³⁰. The ligands for PD-1 (PD-L1 and PD-L2) are constitutively expressed or can be induced in a variety of cell types, including non-hematopoietic tissues, as well as in various tumors^{26,31,32,33}. Both ligands are type I transmembrane receptors containing both IgV- and IgC-like domains in the extracellular region and contain short cytoplasmic regions with no known signaling motifs. Binding of either PD-1 ligand to PD-1 inhibits T-cell activation triggered through the T-cell receptor. PD-L1 is expressed at low levels on various non-hematopoietic tissues, most notably on vascular endothelium, whereas PD-L2 protein is only detectably expressed on antigen-presenting cells found in lymphoid tissue or chronic inflammatory environments. PD-L2 is thought to control immune T-cell activation in lymphoid organs, whereas PD-L1 serves to dampen unwarranted T-cell function in peripheral tissues²⁶. Although healthy organs express little (if any) PD-L1, a variety of cancers were demonstrated to express abundant levels of this T-cell inhibitor. PD-1 has been suggested to regulate tumor-specific T-cell expansion in subjects with melanoma (MEL)³⁴. This suggests that the PD-1/PD-L1 pathway plays a critical role in tumor immune evasion and should be considered an attractive target for therapeutic intervention.

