Pembrolizumab Arm A)	200 mg q every three weeks start on day 1 of cycle 1							
Pembrolizumab Arm B)	200 mg q every three weeks start on day 1 of cycle 2							

a) All screening procedures must be performed within 28 days unless otherwise indicated. Pre-study tests, History and Physical may be used for Day 1 tests if within 2 weeks

- b) Toxicity assessment must be performed until all treatment-related toxicities have been resolved or decreased to grade 1. Adverse events must be recorded up to 30 days after termination on study
- c) Every month for the first 6 cycles, then at least every 3 cycles thereafter, more frequently if clinically indicated
- d) For women of childbearing potential, performed within 7 days of starting treatment. Pregnancy test will be repeated if clinically indicated.
- e) Staging studies within 30 days prior to day of start, restaging after cycle 3 (week 9), 6 (week 18), then 9, 12, then every 6 cycles if clinically indicated. Partial and complete responses must be confirmed at least one month apart from the first documentation of objective response. Scans may be performed more frequently if clinically indicated.
- f) Pre-study within 14 days, and end of cycle 3 (preferably day 17-19) prior to cycle 4 day 1 pembrolizumab infusion.
- g) Cycle delays up to 5 days for non-medical reason (e.g. holidays) are acceptable without notification of regulatory agencies.
- h) On day 10-12 pre-dose.
- i) Sodium, Potassium, Chloride, blood urea nitrogen, Creatinine, Non-fasting glucose, Calcium, Magnesium, Phosphorus, ALT, AST, Alkaline Phosphatase, Albumin, Total Bilirubin, Total Protein
- j) Therapy delay for palliative radiation should be based on discussion with the study sponsor and the treating physician, every effort should be made not to hold therapy, patients where vorinostat is being held for more than 4 weeks may stay on study if there is felt to be a benefit

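### The only planned model with an arm term (exploratory, 8.3.4.1) conditions on Cycle-3 PD-L1, so its arm results cannot be read as the total schedule effect unless arm and PD-L1 are unrelated, which the plan assumes but does not analyse

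*Combined protocol and SAP*

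**What the plan says.** The tumour PD-L1 part of Section 8.3.4.1 classifies PD-L1 as negative or positive at baseline and after cycle 3. It then plans a logistic regression that estimates the Cycle-6 response rate, with its 95% CI, "as a function of study arm and PD-L1 level at baseline and Cycle 3". A selection rule follows: "Either time-point will be eliminated from the model if its effect is weak", with p>0.2 as the cut.

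The same paragraph states three hypotheses. The first is introduced with the words "hypothesizing that delayed pembrolizumab treatment (i.e., Arm A) will increase tumor response". Hypothesis (i) is that PD-L1 expression promotes response. Hypothesis (ii) is that PD-L1 expression will rise "but will not be associated with treatment (because PD-L1 is stimulated by vorinostat not pembrolizumab").

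The study calendar (Table 6, Section 6.2.3) places the second biopsy at the "end of cycle 3 (preferably day 17-19) prior to cycle 4 day 1 pembrolizumab infusion". It starts pembrolizumab in one ER+ arm at "200 mg q every three weeks start on day 1 of cycle 1" and in the other on day 1 of cycle 2.

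No other planned analysis has an arm term:
- Section 8.3.2 is a one-sample rule per arm against 10%.
- The gene and signature models compare responders with non-responders or adjust for clinical factors.
- The Cox models use gene expression.
- The immune endpoints are compared before and after treatment, or by response.

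**The concern.** The two randomised arms differ only in when pembrolizumab starts. A marker measured at the end of cycle 3 is measured after that difference has begun. If the schedule shifts PD-L1, and PD-L1 drives response as hypothesis (i) says, then holding Cycle-3 PD-L1 fixed removes that part of the schedule effect from the arm coefficient. An unmeasured cause of both PD-L1 and response would add bias of its own.

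Adjustment is safe if hypothesis (ii) is true. The written model has response as its outcome, so it cannot check (ii), and no other analysis does. The p>0.2 rule adds a second difficulty: the data decide whether the arm term is adjusted for a post-randomisation marker, so its meaning is not fixed in advance.

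At stake is how the one planned regression that contains arm would be read beside the hypothesis that delayed pembrolizumab increases response. The arm-specific response rates it produces come from the same coefficients and carry the same limitation.

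**Working it through.** **The plan's own figures.** The documents give no figure for the PD-L1 model. The sample size of 29 per arm comes from the Simon design in Section 8 (stop at 0 or 1 of 10, then 29 in total; 10% v 30%). With rejection at 6 or more of 29, the exact two-stage binomial gives alpha 0.0471 and power 0.8051, matching the stated 0.0471 and 80.5%.

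**Timing.** Cycles last 3 weeks, and the biopsy is on about day 17-19 of cycle 3. A cycle-1 start gives doses in cycles 1, 2 and 3, which is three. A cycle-2 start gives doses in cycles 2 and 3, which is two.

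**From model odds ratio (OR) to total OR.** PD-L1 rates and effects are not in the documents, so these inputs are assumptions. Take

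logit(p) = -1.5 + ln(OR_arm) × delayed + ln(OR_PDL1) × PD-L1 positive,

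average p over the assumed PD-L1 positivity in each arm, and form the OR of the two averages.

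Worked case: positivity 60% (early) v 40% (delayed), OR_PDL1 = 4, model OR_arm = 1.5.
- Early: 0.4 × 0.1824 + 0.6 × 0.4716 = 0.3559.
- Delayed: 0.6 × 0.2508 + 0.4 × 0.5724 = 0.3794.
- Total OR: (0.3794/0.6206) / (0.3559/0.6441) = 1.11.

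The same formula for other inputs, always with model OR 1.5:

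| Positivity, early v delayed | OR_PDL1 | Response, early v delayed | Total OR |
|---|---|---|---|
| 60% v 60% | 4 | 35.6% v 44.4% | 1.44 |
| 55% v 50% | 2 | 25.2% v 32.6% | 1.44 |
| 55% v 50% | 4 | 34.2% v 41.2% | 1.35 |
| 60% v 40% | 2 | 25.8% v 31.1% | 1.30 |
| 60% v 40% | 4 | 35.6% v 37.9% | 1.11 |
| 40% v 60% | 4 | 29.8% v 44.4% | 1.88 |

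The first row has no arm difference in PD-L1. Its gap from 1.5 to 1.44 is non-collapsibility of the odds ratio, not mediation. The last row reverses the split, and the model then understates the total effect. With 60% v 40%, OR_PDL1 = 4 and model OR 1.0, the total OR is 0.77.

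**Shared cause.** Suppose an unmeasured factor has OR 4 on both PD-L1 and response, and neither PD-L1 nor schedule affects response. The true total OR is then 1.00. The adjusted OR is 0.92 for a 40% v 60% split and 0.85 for 30% v 70%.

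**Selection rule.** This was simulated at 29 per arm with 10% response in PD-L1-negative patients. The Cycle-3 term was kept in about 12-14% of trials if PD-L1 had no effect, 30-32% if its OR was 2, and 66-74% if its OR was 4. It stays most often when hypothesis (i) is true, which is when conditioning on it matters most.

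**Precision.** At 35.6% v 37.9% with 29 per arm, the standard error of the log OR is √(1/(29 × 0.3559 × 0.6441) + 1/(29 × 0.3794 × 0.6206)) = 0.545. A total OR of 1.11 would have a 95% CI of about 0.38 to 3.2. The shift from 1.5 to 1.11 is about 0.30 on the log scale, roughly half a standard error.

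**The case against.** The strongest case against is that nothing turns on this coefficient. Four parts of it stand.

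- **Purpose.** The analysis is exploratory. Its stated output is response rates by arm and PD-L1 type, and the schedule hypothesis is not explicitly assigned to the arm term.
- **Primary analysis.** Section 8.3.2 already reports each arm's response rate among all patients randomised to it, with a 95% CI, and Section 2.1 ties the optimal approach to that rate. An unadjusted comparison can be formed from those two proportions, although at 24 weeks rather than Cycle 6.
- **Mechanism.** The documents attribute PD-L1 induction to vorinostat, which is scheduled identically in both ER+ arms. Section 1.3.1 explains the benefit of pre-exposure through regulatory T cells and FoxP3. Only one pembrolizumab dose separates the arms at biopsy.
- **Size.** The 60% v 40% split has no source. The response rates of 36-38% that it implies exceed the plan's 30% target.

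A reader might infer that the trial would choose its schedule from this model, so that an inferior schedule could be declared better. The documents do not support that: no decision rule uses the model, and the per-arm rates are reported beside it. A reader might also take Section 1.1.4, "The ligands for PD-1 (PD-L1 and PD-L2) are constitutively expressed or can be induced in a variety of cell types", as evidence that the pembrolizumab schedule changes PD-L1. That sentence is general background and does not rebut hypothesis (ii).

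Two points survive. Hypothesis (ii) is plausible but is assumed rather than analysed, and the selection rule leaves the meaning of the arm term to the data.

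**Conclusion.** The point holds as one of interpretation in an exploratory analysis. The arm term and arm-specific rates in 8.3.4.1 cannot be read as the total effect of schedule unless hypothesis (ii) holds. If (ii) holds, only the small non-collapsibility gap remains. If the Cycle-3 term happens to be dropped, the arm term is close to the total effect, but which of the two is reported then depends on the data.

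The size of the distortion is unknown. Under the assumptions above it runs from slight (1.5 v 1.44) to substantial (1.5 v 1.11), and its direction depends on which arm has more PD-L1 positivity. The larger figures illustrate the mechanism and are not expected values. The primary per-arm analysis is untouched. This is a low-severity improvement to the plan.

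**What to change.** 1. Estimate the schedule contrast in the two randomised ER+ arms only, from a model with arm and baseline PD-L1 and no Cycle-3 term. Arm C is not randomised (Section 3.6) and should not enter this contrast.
2. Assess hypothesis (ii) with a model of Cycle-3 PD-L1 on arm and baseline PD-L1. Report an estimate with its CI rather than a test. For 60% v 40% at 29 per arm, the standard error of the difference is √(2 × 0.24/29) = 0.129, so power is about Φ(0.20/0.129 - 1.96) = 34%. A null result would not show that adjustment is harmless.
3. Keep the Cycle-3 PD-L1 and response model as a separate association analysis. State that its arm term is not the schedule effect.
4. Reconcile the arm labels. Section 8.3.4.1 calls Arm A the delayed arm, while the regimen tables in Section 5.1 and the study calendar start pembrolizumab in Arm A in cycle 1 and in Arm B in cycle 2. Until these agree, the direction of any arm effect cannot be read.

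The statistical changes cost SAP wording and two small models on data already being collected. The primary analysis does not change.

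### The exploratory PD-L1 response model drops a time-point at p>0.2 and then names PD-L1 groups that do not match the model that is left

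*Combined protocol and SAP*

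**What the plan says.** Section 8.3.4.1 (Tumor PD-L1 assessment) scores PD-L1 from 0 to 3 and splits it into negative (0) and positive (1-3). With a value before treatment and another after Cycle 3, "this defines four types of PD-L1 participants: {0,0; 0,1; 1,0; 1,1". The model is "logistic regression to estimate Cycle-6 tumor response rate (95% CI) as a function of study arm and PD-L1 level at baseline and Cycle 3". A selection step follows: "Either time-point will be eliminated from the model if its effect is weak", with weak meaning p>0.2, "leaving two types of PD-L1 participants: either {0,0; 1,1} or {0,0; 0,1". The section does not say whether the two p-values come from one joint fit or from stepwise fits, or what happens if both exceed 0.2. It names no analysis set for this model and has no rule for a missing Cycle-3 biopsy.

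The timing comes from the footnotes to the study calendar (Table 6, section 6.2.3). The on-treatment biopsy is at "end of cycle 3 (preferably day 17-19) prior to cycle 4 day 1 pembrolizumab infusion". Imaging is "restaging after cycle 3 (week 9), 6 (week 18), then 9, 12". Section 8.3.2 defines the primary response as status "SD or better (CR, PR) at 24 weeks".

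**The concern.** Removing a covariate from a logistic model does not remove patients. It merges the patterns that differ only in that covariate. The two printed sets do not describe either possible merger, so an analyst who builds the dataset from this sentence fits something other than the reduced model.

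The rationale (1.3.1) is that vorinostat raises PD-L1, and 8.3.4.1 hypothesises that PD-L1 expression promotes response. The informative contrast is therefore patients who go from negative to positive against those who stay negative. One branch of the rule, read literally, removes those converters. The other removes everyone who was positive at the start. Which branch applies is decided by a p-value in a small sample, and the final intervals are reported as if no selection had taken place.

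A related gap is that Cycle-3 PD-L1 is measured about nine weeks into treatment. A patient must reach the biopsy to have a value, and the model has no landmark definition.

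**Working it through.** **1. The plan's own figures.** The only sample-size figures are for the primary Simon design (n1=10, continue with 2 or more responses, n=29, 10% versus 30%). Declaring activity at 6 or more of 29 reproduces them: alpha 0.0471 and power 0.8051, against the stated 0.0471 and 80.5%. The final cut-off of 6 is inferred, because the plan does not print it. No size or power is stated for the PD-L1 model.

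**2. Correct grouping after one time-point is removed** (first digit baseline, second digit Cycle 3):

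| Covariate dropped | Negative group | Positive group | Patients lost |
|---|---|---|---|
| Cycle 3 | 00, 01 | 10, 11 | none |
| Baseline | 00, 10 | 01, 11 | none |
| Printed set 1 | 00 | 11 | all 01 and 10 |
| Printed set 2 | 00 | 01 | all 10 and 11 |

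In printed set 1 the two time-points agree in every retained patient, so the contrast cannot be assigned to either. In printed set 2 baseline is constant, so it is a Cycle-3 comparison among baseline-negative patients only. Reading the sets as shorthand does not help. If set 2 means that only Cycle 3 varies, its counterpart would be 00 and 10, not 00 and 11. Assuming that no patient goes from positive to negative does not help either, because both correct groupings would still contain 00, 01 and 11.

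**3. Patients lost on the literal reading.** The plan gives no PD-L1 rates, so these are assumed: baseline positive b = 10-50%, conversion from 0 to 1 c = 10-50%, loss from 1 to 0 = 10%. N = 58 is the two randomized arms at full size, with both biopsies assumed available.
- Set 1 loses (1-b)c + 0.1b. With b = c = 0.3: 0.7×0.3 + 0.1×0.3 = 0.24, or 13.9 of 58. Over the range: 10% to 46% (about 6 to 27 patients).
- Set 2 loses b. With b = 0.3: 17.4 of 58. Over the range: 10% to 50% (about 6 to 29 patients).

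**4. How often the screen would drop a real effect.** This is a two-proportion normal approximation at two-sided 0.20 (z = 1.2816), for true response of 10% in PD-L1-negative and 30% in positive patients, with 30% positive. At N = 58 the groups are 40.6 and 17.4, and the pooled rate is (0.1×40.6 + 0.3×17.4)/58 = 0.16.
- Null SE = √[0.16×0.84×(1/40.6 + 1/17.4)] = 0.105.
- Alternative SE = √[0.09/40.6 + 0.21/17.4] = 0.120.
- Retention = Φ[(0.2 - 1.2816×0.105)/0.120] ≈ 0.71, so the time-point is dropped about 29% of the time.
- The same formula gives 40% at N = 40 and 48% at N = 29.

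This ignores adjustment for the other, correlated time-point.

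**5. Behaviour with no PD-L1 effect.** Simulation with N = 58, 30% baseline positive and 10% loss. Both p-values are read from the joint fit, and the model is refitted if one time-point is dropped.

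| Scenario | Both weak | Some PD-L1 term p<0.05 after selection | Same, full model |
|---|---|---|---|
| Response 30%, conversion 30% (5,937 converged fits) | 67.9% | 9.6% | 6.7% |
| Response 20%, conversion 50% (5,737 converged fits) | 68.3% | 7.0% | 5.7% |

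So the case with no rule is the usual one when PD-L1 has no effect. A stepwise order of elimination would give different percentages, and the plan does not fix the order.

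**6. Timing.** Cycle 3 begins after 42 days, so its days 17-19 are study days 59-61. The first scheduled restaging is at week 9, about day 63. Cycle 6 ends at week 18. Scheduled scans fall at weeks 18 and 27, with none at week 24.

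**The case against.** The best defence is that nothing in 8.3.4.1 says patients are excluded. It speaks of removing a time-point from the model, and a model without that covariate uses everyone who has the other one. The braces may be mislabelled groups. That is fair, and the loss in step 3 is therefore conditional on the literal reading. It does not rescue the sentence, which still names the wrong groups.

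Three stronger readings are tempting and are not supported:
- A reader might infer that the rule deletes all converters in either branch. It does not. The set {0,0; 0,1} keeps the 0-to-1 patients and loses the baseline-positive ones.
- A reader might take the median PFS values of 4.3 and 2.3 months in 1.3.1.2 and calculate how many patients progress by week 9 and so lack a Cycle-3 value. Progression by week 9 is not the same as a missing biopsy. At the preferred timing the biopsy precedes the week-9 scan. Sections 3.1, 3.4 and 6.1 let some patients continue despite radiographic progression. The 2.3-month median also belongs to a placebo arm without an HDAC inhibitor, whereas every patient here receives vorinostat. The documents do not allow the number without a biopsy to be estimated.
- A reader might call the Cycle-6 outcome an error because the primary endpoint is at 24 weeks. Week 18 is a scheduled scan and week 24 is not, so an exploratory model may reasonably use it.

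It is also fair that limiting parameters in a small sample is a sensible aim, that 0.2 is a lenient threshold, and that the inflation in step 5 is modest. PD-L1's first place in the tissue list concerns the use of scarce tissue, not inferential weight.

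**Conclusion.** The point holds for the grouping rule. Neither printed set is the result of removing one binary covariate; this follows from the text alone and needs no assumption. If the sets are followed literally, one loses every patient whose PD-L1 changed and the other every baseline-positive patient: 10-46% and 10-50% under the assumed rates, which are not the plan's.

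The selection step is a lesser problem. The 95% intervals become post-selection, with 7.0-9.6% false positives against 5.7-6.7% in the full model in two illustrative scenarios. There is no instruction for two weak time-points, which occurred in about 68% of simulated trials with no effect. The missing landmark definition follows from the timing of the biopsy, and its size cannot be given.

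The analysis is exploratory. The primary response test and its error rates are untouched.

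**What to change.** In 8.3.4.1:
- Delete the p>0.2 elimination rule and the two printed category sets.
- Keep baseline and Cycle-3 PD-L1 in the model whatever their p-values, using all patients with both measurements, and report the 0,1 versus 0,0 contrast with its 95% CI.
- Restrict that model to patients progression-free at the Cycle-3 biopsy. Since the first scheduled scan usually follows the biopsy, define this as no progression documented by the biopsy date. Report how many patients have no Cycle-3 value, and why.
- Fit a separate baseline-only model in all patients with baseline tissue.
- Keep Cycle-6 response as the outcome and report 24-week response as a sensitivity outcome.

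The cost is a change of analysis wording, one more parameter than a reduced model would carry, and a smaller sample for the landmark model. No new procedure is needed: both biopsies are already scheduled, and 24-week status is already required for the primary endpoint.
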